The Safety and Efficacy of the Transnasal Humidified Rapid-Insufflation Ventilatory Exchange (THRIVE) for Laser Laryngeal Surgery

Study Protocol

NCT03086265

August 12, 2016

STUDY PROTOCOL: THRIVE AND LASER LARYNGEAL SURGERY

1

STUDY OBJECTIVES

1. DETERMINING THE SAFETY OF THRIVE FOR LASER LARYNGEAL SURGERY. Current practice involves the use of specialized ETTs or jet ventilation catheter (JVC) that are laser resistant, but not laser proof. One of the major concerns with their use is the possibility of airway fire. The “fire triangle” requires the presence of an oxidizer (O_2), the ignition source (laser) and the “fuel” (ETT or JVC). If high oxygen concentration (FiO_2) is administered to the patient, the airway fire may happen, with devastating consequences. Thus, a decrease in oxygen concentration (FiO_2) below 30% constitutes current standard of care when ETT or JVC are used. Such low FiO_2 may not be well tolerated by all the patients.

In contrast, during THRIVE the fuel source (ETT or JVC) is removed, the “fire triangle” is disrupted, and safe administration of a higher FiO_2 is possible. Importantly, a completely “tubeless”, non-instrumented surgical field will be greatly enlarged, providing superior operating conditions and access to all parts of the glottis. This should improve operating conditions, decrease surgical time, and potentially lead to better patient outcomes. The safety of THRIVE for laser laryngeal surgery has not been formally investigated, and will be explored in this study.

2. DETERMINING THE SAFE DURATION OF THRIVE FOR VOCAL CORD LASER SURGERY. With the patient anesthetized, apneic, and adequately oxygenated with THRIVE, the build up of carbon dioxide in patient’s blood ($PaCO_2$) and ensuing acute hypercapnic acidosis will be the main factors limiting the duration of THRIVE administration. At present, the rate of $PaCO_2$ rise with THRIVE is suggested to be between 1.1 – 1.8 mm Hg per minute. By using the serial ABG measurements, we will be able to determine the rate of $PaCO_2$ rise during THRIVE and provide clinical guidance for safe administration of THRIVE in the future. We will allow $PaCO_2$ to rise to 75 mm Hg, which is considered a safe level for moderate hypercapnia in patients without significant comorbidities (see Exclusion Criteria).

3. DETERMINING THE OPTIMAL VENTILATORY STRATEGY FOR MAINTAINING SAFE $PaCO_2$ LEVEL DURING THRIVE ADMINISTRATION

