ITRAOPERATIVELY. Once $PaCO_2$ has exceeded 75 mm Hg, we will administer either the low-frequency or high-frequency supraglottic jet ventilation (LFJV, HFJV) through the in situ operating surgical laryngoscope, in order to counteract hypercapnia. The administration of JV modality will be conducted in a randomized fashion, and will continue for at least 10 min, or until $PaCO_2$ has decreased below 65 mm Hg,

STUDY PROTOCOL: THRIVE AND LASER LARYNGEAL SURGERY

2

after which THRIVE will be resumed. The comparative efficacy of these two supraglottic JV modalities in eliminating CO₂ in anesthetized patients is unknown. Determining the optimal mode of JV during THRIVE will allow to establish safe anesthetic protocols for future use. To obtain more robust data, we will cross each patient over to an alternative JV modality, if JV needs to be repeated intraoperatively. For example, if a patient started with supraglottic low-frequency JV, the second JV run will be high-frequency, the third low-frequency again, etc. By having the patient serve as a self-control, we should be able to obtain more robust PaCO₂ data and determine better which frequency works best for counteracting THRIVE-induced deliberate hypercapnia.

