 - iii. Surgical time: from picking up suspension laryngoscope to laryngoscope withdrawal
 - iv. Time to suspension: from picking up suspension laryngoscope to full suspension
 - v. Number of required repositions for suspension laryngoscope
 - vi. Lowest SpO_2
 - vii. Total doses of anesthetic drugs used, including vasopressors, etc.
 - viii. PACU recovery profile
 - ix. Functional recovery profile after surgery

STUDY PROTOCOL: THRIVE AND LASER LARYNGEAL SURGERY

OPERATING ROOM PREPARATION

1. All drugs, airway supplies, suction, eye tape, etc. per routine.
2. 5.0 laser ETT with two pre-filled 10 ml NS syringes: use a methylene blue tinged syringe for a proximal cuff.
3. A long pediatric ETT stylet and a pediatric gum-elastic bougie.
4. 5.0 MLT tube for apneic intermittent ventilation (AIV), if required (see protocol, below).
5. Precut large Tegaderm strips for securing ETT to the chin in left corner of patient's mouth.
6. Video laryngoscopy system: either a Glidescope or a Storz CMAC system.
7. Monsoon JV with connection tubing for suspension laryngoscope, and full humidification set up.
8. Sterile tracheal suction catheter assembly for tracheal FiO_2 sampling.
9. Four channel Alaris pump with:
 - a. NS carrier at 50 ml/hr
 - b. Propofol drip
 - c. Remifentanil drip
 - d. Check to assure tight connections throughout
10. IV LR/NS loading 5 ml/kg prior to induction, and 5 ml/kg x 1 as required intraop.
11. 20 ml NS syringe in line for chasing the induction and IVP drugs intraop. **Please minimize total IVF due to high incidence of urinary retention in male patients.**
12. Edwards system.
13. I-STAT with sufficient number of cartridges.
14. Working PNS with pads (make sure the battery is fresh).
15. BIS/Sedline monitor.

STUDY PROTOCOL: THRIVE AND LASER LARYNGEAL SURGERY

	THRIVE GROUP	CONTROL GROUP

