	
 Turn THRIVE to 70 l/min. Maintain jaw thrust, with oral airway as necessary, before surgeon starts suspension laryngoscopy. Continue, as necessary until patient is in full suspension. Suspension laryngoscopy by surgeon in 1 min. 	
 Mask ventilation, if required. Intubate in 1 min with laser 5.0 ETT, using acute angle video laryngoscopy system (Glidescope or Storz D-blade), secure ETT to chin in left corner of the mouth.
MAINTENANCE	
 TIVA + THRIVE (FiO₂ 1.0) at 70 l/min. If SpO₂ < 90%, or ventricular arrhythmias, discuss with surgeon converting to the following options: 
 Supraglottic or Infraglottic JV 5.0 laser ETT 5.0 MLT tube with apneic intermittent ventilation Obtain ABGs per THRIVE protocol. If PaCO₂ > 75 mmHg, randomize patients to JV protocol, and institute JV accordingly. Crossover each patient to an alternative JV frequency for repeated JV rounds. 	
 TIVA + O₂:Air; FiO₂ < 0.3 Mechanical ventilation to normocapnia: EtCO₂ 35-40 mmHg. Vt 8 ml/kg of predicted body weight (PBW), PEEP 5 cmH₂O. PBW Males = 50 + 2.3 (Height" - 60) PBW Females = 45.5 + 2.3 (Height" - 60) FiO₂ < 0.3 unless SpO₂ < 90% (increase FiO₂ to 0.4, and coordinate subsequent FiO₂ decrease with surgeon during laser timeout).
	
 A-line and Edwards monitoring. No NBP monitoring, unless A-line malfunction. BIS-guided TIVA with Propofol/Remifentanil to maintain BIS 40-60. Maintain main IV at TKO. All IV bolus drugs are chased by 15 ml of NS using in-line 20 ml syringe. 	

MAINTENANCE
(cont.)

- **TIVA dosing:**
 - TIVA is carried in by Alaris NS carrier at 50 ml/hr.
 - For normal weight patients, dose Prop/Remi infusions per total body weight.
 - For obese patients (BMI \geq 30), dose Prop/Remi infusions per lean body weight (LBW). **Simplified LBW formula: LBW = IBW x 1.2; IBW = 22 x Ht(m)².**
 - **Starting dose:** Propofol 120 mcg/kg/min, Remifentanil 0.1 mcg/kg/min.
 - **Titratable range:** Propofol 80-150 mcg/kg/min, Remifentanil 0.05-0.3 mcg/kg/min. **Optimize Remifentanil dose first.**
 - Rocuronium boluses 0.15 mg/kg, to maintain 0-1/4 TOF at ulnar nerve.
- **Treating hypertensive responses (MAP $>$ 20 mmHg from preoperative baseline):**
 - Remifentanil 0.5 mcg/kg and Propofol 0.5 mg/kg boluses q 2 min, as required per hemodynamic responses and BIS/Sedline readings

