STUDY PROTOCOL: THRIVE AND LASER LARYNGEAL SURGERY

10

THRIVE PROTOCOL	
PREOP	
• Obtain baseline ABG and i-STAT Troponin I #1.
PREINDUCTION	
• Pre-O₂ with THRIVE (FiO₂ 1.0) at 40 l/min for 5 min.• Maintain patient's head is elevated 30-40° (table in BACK UP position, not reverse Trendelenburg).• Connect OR monitors and Edwards system.• Obtain ABG after 5 min of THRIVE @ 40 l/min.
INDUCTION	
• THRIVE @ 70 l/min.• Maintain jaw thrust, with oral airway as necessary, for 1 min before surgeon starts suspension laryngoscopy.
MAINTENANCE	
• Maintain THRIVE @ 70 l/min.• Obtain tracheal FiO₂ once patient is suspended, before the start of surgery.• Assure fully moistened pledges, and no cotton material/other fuel left in airway before firing the laser.• ABG q 10 min post-induction, until patient resumes spontaneous ventilation.• Once PaCO₂ > 75 mmHg, randomize patients to low-frequency (20 cpm) or high-frequency (150 cpm) supraglottic jet ventilation
○ Settings for either JV modality:
▪ DP (driving pressure, psi) = total body weight x 0.4 (do not exceed 45 psi)▪ FiO₂ 1.0, Inspiratory time 40%, Humidity level: maximum (8)○ Continue JV, checking ABG q 10 min, until PaCO₂ reaches ≤ 65 mmHg, at which point resume THRIVE○ Repeat JV per above, as necessary for PaCO₂ > 75 mmHg. Crossover each patient to an alternative JV frequency for repeated JV rounds.• Obtain tracheal FiO₂ once surgery completed, before withdrawal of suspension laryngoscope.
EMERGENCE	
• Maintain THRIVE at 70 l/min with jaw thrust ± oral airway as required, until return of spontaneous ventilation and consciousness. Mask ventilation, as necessary.• Obtain ABG and i-STAT Troponin I #2 once patient resumes spontaneous ventilation.
PACU	
• Obtain ABG and i-STAT Troponin I #3 one hr after resumption of spontaneous ventilation. Remove A-line.

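### The jet ventilation rule has no step for a patient whose PaCO2 does not fall, and no conversion trigger depends on CO2 or pH

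*Protocol*

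**What the plan says.** - **Accepted level.** Study Objectives 2 lets PaCO2 rise to 75 mm Hg, "which is considered a safe level for moderate hypercapnia in patients without significant comorbidities", and expects a rise under THRIVE of 1.1 to 1.8 mm Hg/min.
- **Start and exit of JV.** The THRIVE Protocol table (Maintenance) draws gases every 10 minutes. Above 75 it randomizes the patient to 20 or 150 cycles per minute, with driving pressure set by body weight and capped at 45 psi. The exit is: "Continue JV, checking ABG q 10 min, until PaCO₂ reaches ≤ 65 mmHg, at which point resume THRIVE".
- **Use of the other frequency.** "Crossover each patient to an alternative JV frequency for repeated JV rounds".
- **Conversion.** The Maintenance row of the main protocol table, THRIVE column, says: "If SpO₂ < 90%, or ventricular arrhythmias, discuss with surgeon converting to the following options". The options are supraglottic or infraglottic JV, a 5.0 laser tube, or a 5.0 MLT tube with apneic intermittent ventilation.
- **Second statement of the exit.** Study Objectives 3 says that JV "will continue for at least 10 min, or until $PaCO_2$ has decreased below 65 mm Hg", after which THRIVE resumes.
- **Equipment.** Operating Room Preparation lists the laser tube, and also: "5.0 MLT tube for apneic intermittent ventilation (AIV), if required (see protocol, below".
- **Analysis.** The SAP gives 20 patients randomized 1:1, so about 10 on THRIVE. It names a t-test and Fisher's exact test, and describes no analysis of the JV modes.

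**The concern.** JV is the protocol's remedy for hypercapnia, yet Study Objectives 3 says that how the two modes compare in clearing CO2 is unknown. A mode that does not work in some patients is therefore foreseeable. Followed as written, the table keeps such a patient on the allotted frequency. It has no PaCO2 ceiling, pH floor, change of settings or switch of frequency within the round, and no CO2 or pH value prompts use of the tube already in the room. The gap begins above 75, the level the protocol calls safe, and the hemodynamic reassurance in Study Objectives 4 is given only up to 70.

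The two statements of the exit also differ. The table requires 65 or less. The objectives text joins a 10-minute duration and the PaCO2 target with an *or*. Time on JV, and so the listed endpoint on CO2 elimination by JV mode, could depend on which page is followed.

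**Working it through.** The plan states no figure to reproduce here. The check compares the rules and then applies the protocol's own rate and gas interval.

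**Inputs from the protocol:** rise 1.1 to 1.8 mm Hg/min; gases every 10 min; JV starts above 75; exit at 65 or less. A linear rise is assumed.

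**1. Highest first reading above 75.** If the preceding gas was 75, the next is 75 + 10 × 1.1 = 86 to 75 + 10 × 1.8 = 93.

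**2. Net fall needed to exit at the next gas.** (start − 65)/10:
- from 75: 1.0 mm Hg/min
- from 86: 2.1 mm Hg/min
- from 93: 2.8 mm Hg/min

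The documents give no JV clearance rate, so whether these are achievable is unknown.

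**3. JV that fails (worst case).** Assume that JV clears no more CO2 than THRIVE:
- after one 10-min block: 86 + 11 = 97 to 93 + 18 = 111
- after two: 97 + 11 = 108 to 111 + 18 = 129

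At each of these gases the table's instruction is still to continue. The documents give no probability for this course.

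**4. pH at those levels.** pH = 6.1 + log10(HCO3/(0.0307 × PaCO2)). Bicarbonate is assumed to be 24 mmol/L, either fixed or rising 1 mmol/L per 10 mm Hg above 40.

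| PaCO2 | HCO3 fixed | HCO3 rising |
|---|---|---|
| 75 | 7.12 | 7.18 |
| 93 | 7.02 | 7.11 |
| 111 | 6.95 | 7.06 |

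**5. Would the saturation trigger catch it?** Alveolar PO2 = 713F − PaCO2 × (F + (1 − F)/0.8), with sea level and a respiratory quotient of 0.8 assumed. At PaCO2 93:
- F = 1.0: 713 − 93 = 620 mm Hg
- F = 0.6 (assumed entrainment): 427.8 − 102.3 = 325.5 mm Hg

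CO2 build-up alone would not bring saturation below 90%. An arrhythmia might occur, but it is a consequence of trouble and not a measure of CO2.

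**6. Effect of the exit wording.** Ten minutes after THRIVE resumes:
- from 65, as the table directs: 65 + 11 = 76 to 65 + 18 = 83
- from 70, as the objectives text could allow: 70 + 11 = 81 to 70 + 18 = 88

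The difference is 5 mm Hg. In general it is the resumption value minus 65.

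**The case against.** The case on the other side has weight in four places.

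**Clinical judgment and monitoring.** Patients have an arterial line, continuous hemodynamics, 10-minute gases, prepared tubes and broad exclusions, and nothing forbids earlier conversion. This is true and lowers the risk. But the protocol does not leave other rescues to judgment: it scripts hypotension drug by drug with repeat doses. The CO2 pathway, which Study Objectives 2 names as the main limit on THRIVE, has the measurements and the equipment but no rule joining them.

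**The exit wording.** A reader might infer that the protocol contains two contradictory exit rules. The documents do not support that firmly. The objectives text is narrative, and its duration is phrased as a minimum. With 10-minute gases, 10 minutes is the practical minimum anyway. Returning a patient to apnea with PaCO2 still high would also defeat the stated purpose of JV. The wording is loose and should be aligned, but its effect is small (step 6).

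**The crossover data.** A reader might infer that each failed first round costs one crossover patient. That is true only if the patient would otherwise have reached a second round. With an assumed baseline of 40, the first gas above 75 falls at about 20 to 40 minutes. Allowing 10 minutes of JV and 10 of THRIVE, round two starts no earlier than about 40 to 60 minutes after induction. Surgical duration is not given, so the loss cannot be counted. Crossover was always conditional on needing repeat JV, and a failure rule would not restore those rounds.

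**Slow but working JV.** At an assumed net fall of 0.5 mm Hg/min, going from 93 to 65 takes 28/0.5 = 56 minutes. Continuing is then correct, so a long round is not in itself evidence of the gap. The trigger should rest on direction and level, not on time alone.

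**Conclusion.** The concern holds in a limited form. The operating rule has no step for JV that does not lower PaCO2, and the stated conversion triggers do not track CO2 on FiO2 1.0. That much rests on the text alone. The 86 to 93 upper range for the first reading above 75 uses only the protocol's rate and gas interval, with a linear rise. The 97 to 111 range after 10 minutes of JV further assumes that JV does no better than THRIVE. It shows how far the rule reaches and does not forecast what patients will experience. The pH and alveolar PO2 figures rest on the assumptions stated with them.

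The exit wording is a secondary point. The randomized first-round comparison of JV modes and the estimate of PaCO2 rise before JV are not undermined. This is mainly a gap in patient management with a reporting consequence, and it deserves correction because the correction is short.

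**What to change.** **(a) One exit rule.** Put the table's criterion, PaCO2 65 or less, into Study Objectives 3. It governs resumption of THRIVE during surgery; the Emergence row, which already provides for mask ventilation, stays as it is.

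**(b) A JV-failure trigger,** added to the conversion triggers in the Maintenance row. It is met when a 10-minute gas during JV shows PaCO2 still above 75 and not lower than the previous value, or when a PaCO2 ceiling or pH floor set by the investigator is crossed. The patient is then converted to the 5.0 laser tube, with FiO2 below 0.3 before the laser is fired, as in the control group. Study Objectives 1 says that FiO2 "below 30% constitutes current standard of care when ETT or JVC are used". The MLT tube is used only for apneic intermittent ventilation, as listed, and is removed before lasing. In the worst case of step 3, the trigger is met at the first gas on JV and avoids the further 11 to 18 mm Hg of a second block.

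**(c) Reporting.** List each THRIVE patient's highest PaCO2, lowest pH and any conversion. Count rounds that meet the trigger as failures of that JV mode. Show the randomized first-round comparison separately from crossover rounds, and state that the latter come only from patients who needed repeat JV.

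**Cost.** A few lines of protocol text, equipment already in the room, and one small table from gases already drawn. Some patients will be intubated earlier and contribute fewer JV rounds, and a tube brings back the oxygen limit and a narrower surgical field. The SAP is written in the past tense. If the protocol is closed, only (c) applies, labelled post hoc.

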The Safety and Efficacy of the Transnasal Humidified Rapid-Insufflation Ventilatory Exchange (THRIVE) for Laser Laryngeal Surgery

Statistical Analysis Plan

NCT03086265

February 24, 2020

The planned sample size for the study was 40 patients (subsequently reduced to 20 due to logistical constraints), randomized 1:1 to receive one of 2 oxygen delivery systems, Transnasal Humidified Rapid- Insufflation Ventilatory Exchange (THRIVE), or endotracheal tube (standard of care).

Anesthesia, surgical, and patient recovery outcomes were summarized using descriptive statistics, with p-values calculated using a 2-sided t-test and Fisher Exact test.

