6. Patients with electrolyte (K+, Ca++) abnormalities, as determined by the lab values outside of a normal range.
7. Patients with the history or symptoms of increased intracranial pressure or reduced intracranial compliance (e.g. headaches, nausea and vomiting, visual changes, mental changes).
8. Patients with skull base defects.
9. Patients with pulmonary hypertension who have pulmonary artery pressures above the normal range.
10. Patients with significant chronic obstructive or restrictive lung diseases, as manifested by known history of baseline chronic hypoxia and/or hypercapnia, and/or baseline room air SpO₂ < 95%.
11. Obese patients with BMI > 35 kg/m².
12. Patients with severe and poorly controlled gastroesophageal reflux disease despite medical treatment.
13. Patients with hiatal hernia and full stomach patients.
14. Patients on immunosuppressive medications.
15. Patient's refusal to participate in the study.
16. Patients who do not understand English or mentally handicapped.
17. Pregnant or breastfeeding patients.

STUDY PROTOCOL: THRIVE AND LASER LARYNGEAL SURGERY

PROTOCOL AT A GLANCE AND STUDY END-POINTS

18. Patients will be randomly assigned to either THRIVE or Control group (conventional management with laser ETT or jet ventilation catheter – infraglottic jet ventilation – if required). Patients within THRIVE group will be further randomly assigned to either low- or high-frequency supraglottic JV for intraoperative $\text{PaCO}_2 > 75 \text{ mmHg}$.
19. Patients in both groups will have peripheral A-line started prior to induction. Central hemodynamic parameters will be monitored using Edwards system.
20. Patients in THRIVE group will be monitored with serial ABGs, to determine changes in PaO_2 , PaCO_2 , and electrolytes.
21. Anesthetic management is standardized for both groups.
- 22. For both groups, and particularly for THRIVE, assure fully moistened pledgets, and no cotton material/other fuel left in airway before firing the laser.**
23. Study end-points:
 - a. THRIVE GROUP
 - i. Changes in PaO_2 , PaCO_2 , pH, electrolytes, and FiO_2 (tracheal)
 - ii. Hemodynamic changes during permissive hypercapnia
 - iii. Comparative effectiveness of JV modalities on CO_2 elimination
 - iv. Comparative effect of JV modalities on hemodynamics during permissive hypercapnia
 - b. BOTH GROUPS
 - i. Total apnea time
 - ii. Anesthesia time: from induction to awake (opening eyes to command)

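### The SAP plans unadjusted p-values across all between-arm outcome families, with no primary outcome, no confidence intervals and no exploratory label

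*SAP*

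**What the plan says.** The SAP states a sample size of 40, reduced to 20 for logistical reasons, with 1:1 randomization. One analysis sentence follows. It covers three broad families of outcomes ("Anesthesia, surgical, and patient recovery outcomes were summarized using descriptive statistics, with p-values calculated") and ends "with p-values calculated using a 2-sided t-test and Fisher Exact test". It does not list the outcomes within each family or say which test goes with which outcome.

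The between-arm end-points are in the protocol, Protocol at a Glance and Study End-Points, item 23.b. The list runs from "i. Total apnea time" to "ix. Functional recovery profile after surgery", nine items in all. Three of them can hold more than one variable: "Total doses of anesthetic drugs used, including vasopressors, etc", "viii. PACU recovery profile" and the functional recovery profile. The four end-points in item 23.a concern the THRIVE arm only and are not counted here.

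Neither document ranks the end-points, gives a significance threshold, mentions multiplicity or plans an interval estimate.

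**The concern.** The plan's only between-arm inference is a set of p-values, with no rule for which of them carries the conclusion. That leaves two errors open.

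- **A chance finding is promoted.** With many tests and no hierarchy, one small p-value can be reported as a benefit or harm of THRIVE when none exists.
- **A null finding is over-read.** In a trial titled as a study of safety and efficacy, a p-value above 0.05 from 10 patients per arm can pass for evidence that the two techniques perform alike. Without an interval, the reader cannot see how large a difference remains possible.

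The end-points also overlap. Surgical time and time to suspension start at the same moment, when the suspension laryngoscope is picked up, so the second is contained in the first. One difference could therefore appear as two significant results.

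**Working it through.** **Inputs from the documents.** 20 patients randomized 1:1, so 10 per arm (SAP). Nine both-group end-points (protocol, item 23.b). Two-sided t-test and Fisher's exact test, with no adjustment mentioned (SAP).

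**Inputs that are assumptions.** The significance level is not stated; 0.05 is assumed, with a range of 0.01 to 0.10. The correlation between end-points is not stated; 0 to 0.9 is shown. One test per list item is assumed, then varied.

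**The plan's own figure.** Neither 40 nor 20 can be reproduced, because no significance level, power, effect size or SD is given.

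**Step 1: independent tests.** The chance of at least one false positive in k tests at level α is 1 − (1 − α)^k.

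| Case | Calculation | Result |
|---|---|---|
| Nine items, α = 0.05 | 1 − 0.95^9 | 37.0% |
| Eight items (without total apnea time), α = 0.05 | 1 − 0.95^8 | 33.7% |
| Nine items, α = 0.01 | 1 − 0.99^9 | 8.6% |
| Nine items, α = 0.10 | 1 − 0.90^9 | 61.3% |

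Total apnea time is removed in the second row because the protocol's Maintenance table compares an apneic technique with mechanical ventilation. A small p-value there would not be a false positive.

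**Step 2: correlated tests.** Independence is implausible. Time to suspension lies within surgical time, anesthesia time (induction to awakening) spans surgical time, and infused drug totals grow with duration. Simulating nine equally correlated t-tests at 10 per arm and α = 0.05 (60,000 runs per setting) gave:

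| Correlation | At least one p < 0.05 |
|---|---|
| 0 | 37.1% |
| 0.3 | 33.1% |
| 0.5 | 28.2% |
| 0.7 | 20.9% |
| 0.9 | 13.0% |

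The first row agrees with the exact 37.0%.

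**Step 3: Fisher's test.** By full enumeration at 10 per arm, the true size at nominal 0.05 is 0.001, 0.012 and 0.013 for event rates of 0.1, 0.3 and 0.5. Items tested this way add little.

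**Step 4: bundled items.** If the three bundles yield several tests each, k exceeds nine. With independence and α = 0.05:

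- 12 tests: 1 − 0.95^12 = 46.0%
- 15 tests: 1 − 0.95^15 = 53.7%
- 20 tests: 1 − 0.95^20 = 64.2%

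**Step 5: what a non-significant result excludes.** The 95% CI half-width for a mean difference, in units of the pooled SD, is t(0.975, 18) × √(2/10) = 2.101 × 0.447 = 0.94. An observed difference of zero is thus compatible with a true difference of up to 0.94 SD in either direction. An observed difference of 0.5 SD, not significant, has an interval from 0.50 − 0.94 = −0.44 to 0.50 + 0.94 = 1.44 SD. For 80% power the true difference must be 1.32 SD at two-sided 0.05, or 1.81 SD at 0.05/9.

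**The case against.** The strongest reply is that this is a small descriptive comparison. The SAP states no hypothesis, threshold or decision rule, so taken literally it declares nothing significant. That is fair as far as it goes. But the sentence adds p-values to the descriptive summary without calling them exploratory, and supplies no interval beside them. If a descriptive reading is intended, the SAP needs to say so.

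A second reply is that 37% is not a property of this plan. That stands. A reader might take it as the plan's false-positive rate, but it requires a significance level that neither document states, exactly one test per item, and an independence that the end-point definitions contradict. Nor does the SAP say that every item in 23.b is tested; that is a reasonable reading of its three families, not a stated fact. Functional recovery might also reduce to one score, since the protocol collects the QoR15 before and after surgery.

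A third reply is that no passage says a non-significant p-value will be used to claim equivalence. That is also correct: the protocol's hope of offering an alternative to conventional management is conditional on demonstrating safety and efficacy, and is not tied to any test. The risk lies in what the plan permits, not in what it announces.

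A reader might also infer that surgical time is the natural primary outcome, because Study Objective 1 says of the tubeless field: "This should improve operating conditions, decrease surgical time, and potentially lead to better patient outcomes". The documents do not support this. The sentence predicts three things. Operating conditions have listed measures too, such as time to suspension and number of repositions, and the objective itself is headed as a safety objective. The SAP is dated February 24, 2020 and written in the past tense, so a primary outcome chosen now could not be shown to be pre-specified.

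**Conclusion.** The concern holds in a qualified form. The plan spreads unadjusted p-values over three outcome families with no primary outcome, no intervals and no exploratory label.

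The size of the false-positive problem cannot be fixed at one number. At an assumed 0.05 with one test per item, it is about 37% for nine independent tests, 34% without total apnea time, and roughly 13% to 33% for nine t-tests with correlation 0.9 to 0.3. The unknown share of Fisher-tested items pulls it down and the bundled items push it up. Even at correlation 0.9, the nine-t-test figure is more than twice the nominal 5%, so the conclusion does not depend on 37%.

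The precision problem needs no assumption about multiplicity: at 10 per arm, a non-significant t-test leaves differences of about 1 SD open. These points support a change to the reporting rule. They do not show that any particular result is false.

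**What to change.** Amend the SAP as follows.

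1. List the outcomes to be compared between arms from item 23.b, including the components of the three bundled items.
2. Report each as a between-arm difference with a 95% CI: a mean difference for continuous outcomes and a risk difference for binary ones.
3. Label all between-arm comparisons, and any p-values kept, as exploratory and unadjusted for multiplicity.
4. State that no claim of benefit, harm or equivalence will rest on a p-value falling above or below a threshold.
5. Do not name surgical time as a confirmatory primary outcome. If it is highlighted because the 2016 protocol predicted a reduction, disclose the choice as post hoc.

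A multiplicity adjustment is a poorer remedy here. With nine tests at 0.05/9, 80% power would need a 1.81 SD difference, and the set of tests would still be chosen after the fact.

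The cost is SAP wording and a few interval calculations, with no new data. The sponsor gives up significance claims on these outcomes.
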